14.2 Procedures for recording adverse events

Subjects will be carefully monitored for AEs. The investigator or delegate will question the subjects about AEs using a non-leading question, such as ‘How are you feeling?’. The investigator will also record AEs reported spontaneously by the subjects. Clinically significant changes in the findings of physical examination, and clinically significant abnormalities in the results of objective tests (eg laboratory variables, ECG) may also be recorded as AEs. Nasal tolerability questionnaire scores > 0 will be recorded as AEs.

The investigator will use the following criteria when deciding whether to report an abnormal result as an AE.

1. The test result is associated with accompanying symptoms.
2. Results of additional diagnostic tests cause concern or necessitate medical intervention.
3. As a consequence of the test result, the subject is withdrawn, or the subject is given concomitant treatment.
4. The investigator considers the result to constitute an AE.

If any of the above criteria are met, the investigator will report the result as an AE.

A record will be kept in the source documents of all AEs as reported, whether believed to be related or unrelated to the treatment. The record will include the following.

- **Clinical symptoms:** a simple, brief description.
- **Date and time of onset and end:** of clinical symptoms.
- **Frequency:** constant or intermittent.
- **Severity.** The following categories will be used:

Mild: the AE does not interfere with the volunteer's daily routine and does not require intervention; it causes slight discomfort.

Moderate: the AE interferes with some aspects of the volunteer's routine, or requires intervention, but is not damaging to health; it causes moderate discomfort.

Severe: the AE results in alteration, discomfort or disability which is clearly damaging to health.

- **Relationship to treatment:** the assessment of relationship of AEs to the administration of IMP is a clinical decision based on all available information at the time of the completion of the case report form. The following categories will be used.

Related

An event for which, after careful medical evaluation, a connection with trial medication cannot be ruled out with certainty. The event occurs after exposure to trial medication. The event may occur at a reasonable time in relation to the time of administration of the trial medication but might also be attributable to a commonly occurring alternative cause. Alternatively, the event may not occur at a reasonable time in relation to the time of administration of trial medication but may not be attributable to an alternative cause.

Not related

An event which occurs before exposure to the trial medication, or which does not occur at a reasonable time in relation to the time of administration of trial medication and can be attributed to a commonly occurring alternative cause. Alternatively, the event is unrelated to the trial (eg road traffic accident), unless it can be demonstrated that the treatment could have caused the event.

- **Action taken:** none, drug treatment, subject withdrawn, other (specified).
- **Outcome:** recovered/resolved, recovering/resolving (or not recovered/not resolved), or unknown.

14.3 Procedures for dealing with serious adverse events

In the event of any SAE which, in the investigator's opinion, justifies termination or modification of the trial (see section 8.4), dosing will be stopped and the sponsor's responsible physician will be informed immediately (within 24 h of the investigator becoming aware of the event) by telephone or email, as follows.

Sponsor's
responsible
physician:

Tel:

Email:

All SAEs occurring after the signing of the ICF until the follow up visit, regardless of study drug relationship, must be reported to the sponsor's pharmacovigilance provider, with as much information as possible, within 24 h of the investigator becoming aware of the event. The investigator will complete a serious adverse event form and provide it to the sponsor's pharmacovigilance (PV) provider immediately (and within 24 hours of becoming aware of the event), via the following contact details.

Diamond PV Services Limited

Email (primary): [contact]
Fax (back-up): [contact]
Tel (back-up): [contact]

The sponsor will also be notified by email [REDACTED]

The investigator will notify the REC of SAEs that occur during this trial, if applicable, in accordance with the SOPs issued by the Research Ethics Service (RES).

The sponsor is responsible for determining the expectedness of the event, using the reference safety information in the IB. The sponsor will notify the MHRA of all suspected unexpected serious adverse reactions (SUSARs) and will be responsible for ensuring that the REC is notified of SUSARs, if applicable. SUSARs that are fatal or life-threatening must be notified to the MHRA and REC within 7 days after the sponsor has learned of them. Other SUSARs must be reported to the REC and MHRA within 15 days after the sponsor has learned of them.

14.4 Procedures for handling withdrawals due to adverse events

The investigator will assess the reason for withdrawal as far as possible and will fully record the circumstances and medical details. Provided that subjects give written

informed consent, they will undergo the standard medical examination and laboratory tests at withdrawal from the trial which they would have undergone had they completed it (see also section 9.4).

14.5 Procedures for reporting pregnancies

Subjects will be asked to follow the contraception guidance in section 11.

If, during the study, the investigator becomes aware of a pregnancy in a subject or their partner, they will inform the sponsor's pharmacovigilance provider immediately (within 24 h of the investigator becoming aware of the event), as follows.

Diamond PV services Limited

Email (primary): [contact]

Fax (back-up): [contact]

Tel (back-up): Tel (back-up): [contact]

The investigator will follow-up the pregnancy according to HMR SOPs, provided the subject (or their partner) consents to that. A pregnancy will not constitute an SAE unless it meets one of the criteria in section 14.1.

15 Data management and quality assurance

CRF source documents will be securely stored within HMR. Data collected in source documents (see section 18.2) will be transcribed into an electronic CRF (eCRF).

The investigator is responsible for ensuring the accuracy and completeness of the data entered into the eCRF, and the timeliness of data entry. Clinical data (including AEs, concomitant medication, etc) will be entered into a 21 CFR Part 11-compliant Medrio M-1 database. The Medrio M-1 system includes password protection and internal quality checks, such as automatic range checks, to identify data that appear inconsistent, incomplete, or inaccurate. Data reported in the eCRF, derived from source documents, should be consistent with the source documents or the discrepancies should be explained. Where the data violate data validation checks, queries will be generated for resolution by clinical staff. All edits made to the database upon resolution of queries will be recorded in an electronic audit trail.

The database will be locked after the following have been completed: all expected eCRF data have been entered and accounted for; all discrepancies have been resolved; data have been coded as appropriate; SAEs have been reconciled; all site audit findings impacting the database have been closed; and quality control (QC) inspection has been completed.

Data in source documents will be checked by the HMR Quality Assurance (QA) Department. In addition, the HMR QA Department will audit the trial report; that

audit will include checks to ensure that statistical output is correctly reproduced in the report. If requested, the investigator will provide the sponsor, MHRA, and REC with direct access to the original source documents.

16 Statistical methods

16.1 Statistical methods

16.1.1 *Planned analyses*

Final statistical analysis will be done by HMR. A statistical analysis plan (SAP) will be prepared by the HMR Statistics and Data Management Department after completion of the final protocol and before first database lock.

All statistical analysis and reporting will be done using SAS 9.4.

16.1.2 *Statistical hypotheses*

The trial is an exploratory one, and there are no null hypotheses to be tested.

16.1.3 *Analysis populations*

The following populations will be identified:

Safety population: All subjects who received at least 1 dose of study drug.

PK concentration population: All subjects who received at least 1 dose of study drug and for whom a PK sample has been analysed.

PK parameter population: All subjects in the PK concentration population for whom PK parameters can be derived.

PD population: All subjects in the safety population for whom a PD measure is available.

Immunogenicity population: All subjects who received at least 1 dose of study drug and for whom an ADA sample has been analysed (Part B only).

The primary endpoints will be analysed using the safety population for each study part.

In all populations, treatment will be assigned based upon the treatment subjects actually received, regardless of the treatment to which they were randomised.

16.1.4 General considerations for data analyses

The minimum set of summary statistics for numeric variables will be: n, mean, standard deviation (or standard error), median, minimum, and maximum. 95% confidence intervals will be presented where appropriate for data interpretation.

Categorical data will be summarised in frequency tables with n and percentage. Summaries of a categorical variable will include all recorded values.

The minimum and maximum values will be presented to the same number of decimal places as the raw data collected in the CRF (or to 3 significant figures for derived parameters). The mean, median and percentiles (eg Q1, and Q3) will be presented to one additional decimal place. The standard deviation and standard error will be presented to 2 additional decimal places.

'Baseline' will be the latest value obtained before IMP administration (predose on Day 1, or Day -1 if not recorded at predose, or screening if not recorded at predose or on Day -1 [eg weight]). Out-of-range laboratory tests may be repeated. If a test is out of-range at baseline and repeated before dosing, the latest repeat value before dosing will be used as baseline. However, if a test is out-of-range and repeated at any other time during the study, the out-of-range value (not the repeat value) will be included in statistical summaries.

16.1.5 Study population analyses

16.1.5.1 Disposition of subjects

The disposition of all subjects in the safety population will be summarised including: number of subjects randomised; number completing the study, by treatment; and number discontinued from the study.

All subjects who withdraw or are withdrawn from the study will be listed, by treatment, with the reason for withdrawal.

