8.1.1 Part A

Enrolment of up to 36 healthy subjects is planned, in up to 5 groups (Groups A1–A5). Groups A1–A3 will consist of 6 subjects each, and Groups A4 and A5 will consist of 9 subjects each.

Subjects will receive a single intranasal dose of Neumifil or placebo. In Groups A1–A3, 4 subjects will receive Neumifil and 2 will receive matching placebo. In Groups A4 and A5, 6 subjects will receive Neumifil and 3 will receive matching placebo. Additional dose levels may be explored in up to 2 optional groups of up to 9 subjects each.

The starting dose for Group A1 is 0.028 mg Neumifil. Subsequent planned doses are given in Table 3.

Table 3 Planned doses in Part A

Group	Planned nominal dose of Neumifil	Number of subjects	Number on placebo
A1	0.028 mg	6	2
A2	0.085 mg	6	2
A3	0.28 mg	6	2
A4	0.885 mg	9	3
A5	2.8 mg	9	3
A6 (optional)	To be decided	9	3
A7 (optional)	To be decided	9	3

Because Neumifil has never been given to humans before, each new ascending dose will be staggered: sentinel subjects will be dosed first, and the remaining subjects will be dosed at least 23 h later. To maintain the blind nature of the study, the 2 sentinel subjects will be randomised to ensure that 1 subject receives active treatment and the other receives placebo. Since 1 subject will receive placebo treatment, the sentinel subjects may be dosed at least 5 min apart. Provided the investigator considers the safety and tolerability in the sentinel subjects to have been acceptable, the remaining subjects will be dosed, at intervals of at least 10 min.

The planned dose levels may be changed, depending on the safety and tolerability results after previous doses, as described in section 8.5. The dose will not be escalated unless the safety and tolerability of the previous dose is acceptable. There will be an appropriate interval between sequential groups, to allow for review of those data. If the dose level selected is no higher than one that has already been shown to cause no safety concerns, sentinel subjects will not be required, and subjects will be dosed at intervals of at least 10 min. The maximum dose will not exceed 2.8 mg.

Subjects will be screened within 35 days before their dose of trial medication.

Subjects will be resident on ward from 1 day before their dose (Day –1) until about 24 h after dosing (Day 2). They will return for a follow-up visit 7–8 days after their dose (Day 8–9).

8.1.2 *Part B*

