9.3 Exclusion criteria

1. Woman who is pregnant or lactating, or pre-menopausal woman who is sexually active and not using a reliable method of contraception (see section 11).
2. Clinically relevant abnormal medical history, physical findings, ECG, or laboratory values at the pre-trial screening assessment that in the opinion of the

investigator could interfere with the objectives of the trial or the safety of the volunteer.

3. Presence or history of acute or chronic illness sufficient to invalidate the volunteer's participation in the trial or make it unnecessarily hazardous.
4. Presence or history of respiratory disease, including (but not limited to) asthma, chronic obstructive pulmonary disease (COPD), cystic fibrosis, emphysema, requiring acute or chronic medication.
5. Presence of nasal polyps or significant nasal abnormalities.
6. Symptoms of respiratory illness (including, but not limited to, runny nose, sore throat, sneezing, coughing or wheezing) at the screening visit or before dosing on Day 1.
7. Tympanic temperature $> 37.5^{\circ}\text{C}$ at the screening visit or before dosing on Day 1.
8. Impaired endocrine, thyroid, hepatic, respiratory or renal function, diabetes mellitus, coronary heart disease, or history of any psychotic mental illness.
9. History of psychiatric disease, as determine by the investigator.
10. History or presence of malignant disease.
11. Immune-suppressed status, resulting from either disease or medication, as determined by the investigator.
12. Presence or history of severe adverse reaction to any drug or the excipients of Neumifil.
13. Known allergy to tetracycline antibiotics.
14. Use of a prescription medicine (except HRT in female subjects), including oral contraceptives, during the 28 days before the first dose of trial medication, or use of an over-the-counter medicine, with the exception of acetaminophen (paracetamol) and vitamin or nutritional supplements, during the 7 days before the first dose of trial medication.
15. Receipt of an investigational product (including prescription medicines) as part of another clinical trial within the 3 months before admission to this study; in the follow-up period of another clinical trial at the time of screening for this study.
16. Receipt of a COVID-19 vaccine within 7 days before the first dose of trial medication, or anticipate receiving a COVID-19 vaccine within the 7 days after a (final) dose of trial medication.

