10.5 Method of assigning subjects to treatment groups

Volunteers will be assigned a unique screening number, from 001 onward, at their screening visit. After passing all of the screening assessments, subjects will be allocated to study part and group, as described below, according to their availability and the scheduled trial dates.

Subjects will be numbered consecutively, in the order in which they arrive on the ward and are entered into the trial. Subject numbers are presented in Table 4. Subject numbers will be allocated to treatments (active or placebo) according to a randomisation schedule prepared by an independent HMR statistician, using a SAS program.

Subject numbers, and sentinel subject numbers for Part A, are provided in Table 4; at each dose level, subjects will receive active or placebo treatment as described in section 8.1.

Randomisation is described further in section 8.1.

Table 4 Subject and sentinel numbers

Study part	Group	Subject numbers	Sentinel subjects
A	A1	1001–1006	1001 and 1002
	A2	1007–1012	1007 and 1008
	A3	1013–1018	1013 and 1014
	A4	1019–1027	1019 and 1020
	A5	1028–1036	1028 and 1029
	A6*	1037–1045	1037 and 1038
	A7*	1046–1054	1046 and 1047
B	B1	2001–2008	–
	B2	2009–2016	–
	B3	2017–2024	–
	B4*	2025–2032	–

* optional groups.

Replacements for withdrawn subjects will be given a number equal to that of the subject that they replaced plus 100. So, Subject 1001 would be replaced by Subject 1101, and Subject 2025 would be replaced by Subject 2125, and so on.

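### The disposition summary counts subjects randomised within the safety population, so it cannot show anyone who was randomised but not dosed

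*Combined protocol and SAP*

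**What the plan says.** Section 16.1.5.1 defines the disposition summary: "The disposition of all subjects in the safety population will be summarised including: number of subjects randomised". It also asks for the numbers completing and discontinued. Section 16.1.3 gives the denominator: "Safety population: All subjects who received at least 1 dose of study drug". The other four populations in that section (PK concentration, PK parameter, PD, immunogenicity) also require dosing, directly or through a parent population. No randomised or enrolled set is defined.

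Two further sentences bear on the point. Section 16.1.5.1 goes on: "All subjects who withdraw or are withdrawn from the study will be listed, by treatment, with the reason for withdrawal". That listing is not tied to the safety population. Section 16.1.3 adds that in all populations "treatment will be assigned based upon the treatment subjects actually received, regardless of the treatment to which they were randomised".

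On allocation, section 10.5 says: "Subjects will be numbered consecutively, in the order in which they arrive on the ward and are entered into the trial". The randomisation schedule is keyed to that number. Sections 8.1.1 and 8.1.2 have subjects on the ward from the day before their dose.

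Two later steps can stop a dose:
- In both parts, exclusion criteria 6 and 7 (section 9.3) apply "at the screening visit or before dosing on Day 1".
- In Part A groups with sentinels, section 8.1.1 says: "Provided the investigator considers the safety and tolerability in the sentinel subjects to have been acceptable, the remaining subjects will be dosed", and this is at least 23 h after the sentinels.

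**The concern.** A disposition table accounts for subjects from randomisation to the end of the trial. It should let a reader see how many were randomised, how many of those were not dosed and why, and how many completed. If the starting set is dosed subjects only, the first two steps collapse into one. A row labelled as the number randomised then reports the number dosed.

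The row is right as long as every randomised subject is dosed. It goes wrong when someone is stopped between allocation and dosing, and in a first-in-human escalation study that is when the accounting matters most. A dose group halted after its sentinels would be reported as fully dosed relative to its own stated number randomised. Replacement adds to this: under sections 9.4.3 and 10.5 a replacement takes over the withdrawn subject's treatment under a new number. If an undosed subject were replaced, the summary would count only the replacement.

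**Working it through.** **Inputs**
- Part A group sizes (section 8.1.1, Table 3): 6, 6, 6, 9, 9. Part B group sizes (section 8.1.2): 8, 8, 8.
- Sentinels (section 8.1.1, Table 4): 2 per Part A group, none listed for Part B.
- Disposition set (sections 16.1.5.1 and 16.1.3): dosed subjects.

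**The plan's own figure.** 3 × 6 + 2 × 9 = 36 in Part A and 3 × 8 = 24 in Part B, total 60. This matches section 9.1. It is a sum of group sizes; section 16.2 gives no sample size calculation.

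**Step 1, logic.** Let R be the randomised subjects and D the dosed subjects. The summary counts members of R that are also in D. If every dosed subject was randomised, that count is D, so randomised minus dosed is 0 in the table whatever happened in the trial.

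**Step 2, can R be larger than D?** The schedules in sections 12.1.1 and 12.1.2 mark the eligibility check at screening, on Day –1, and again before dosing (Part A) or on Day 1 (Part B). If numbering takes place on arrival on Day –1, a Day 1 failure is a randomised, undosed subject. In Part A, if the remaining subjects are dosed the day after the sentinels, their own Day –1 is the sentinels' dosing day. They would then normally be on the ward, and numbered, before the sentinel decision. Section 8.5.1 itself provides for fewer subjects than planned being dosed. The time of numbering is an inference from these passages; no passage states it.

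**Step 3, size if a Part A group is halted after its sentinels and the rest were already numbered.** Omitted = group size − 2.
- A1–A3: 6 − 2 = 4; 4/6 = 67%. The table shows 2 randomised instead of 6.
- A4–A5: 9 − 2 = 7; 7/9 = 78%. The table shows 2 randomised instead of 9.

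As a share of all Part A subjects randomised by then, with earlier groups fully dosed:

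| Halt at | Randomised | Shown | Omitted | Share |
|---|---|---|---|---|
| A1 | 6 | 2 | 4 | 67% |
| A2 | 12 | 8 | 4 | 33% |
| A3 | 18 | 14 | 4 | 22% |
| A4 | 27 | 20 | 7 | 26% |
| A5 | 36 | 29 | 7 | 19% |

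**Step 4, size of one Day 1 failure, on the same timing assumption.** 1/6 = 17% of a group of 6; 1/8 = 12.5% of a Part B group; 1/9 = 11% of a group of 9.

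**Step 5, does the withdrawal listing close the gap?** It can include an undosed subject who is recorded as withdrawn. It does not give the number randomised. It is arranged by treatment, and treatment means treatment received, which an undosed subject does not have. The protocol does not say whether members of a halted group who were never dosed count as withdrawn.

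**The case against.** A reader might infer that undosed subjects vanish from the report altogether, or that disposition is the only place where a truncated dose level would show. The protocol supports neither. The withdrawal listing is open to subjects outside the safety population. Planned group sizes are fixed in Tables 3 and 4, so a group with 2 dosed would stand out in the counts of the by-treatment summaries (sections 16.1.6.2 and 16.1.6.3) and in the list of dosing dates and times (section 16.1.5.3). Dose decisions by the Safety Review Group are documented (section 8.5.1), and a replacement number marks the subject replaced. The two sentinels, who carry the safety information, stay in every safety table.

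The timing can also be challenged. Section 10.5 ties numbering to arrival and to entry into the trial, which fixes an order and not a time. Section 12 mentions the trial number after saying that only eligible subjects may be enrolled. On that reading, someone who fails criterion 6 or 7 on Day 1 may never have been randomised, and the Day 1 loss would be zero. The sentinel figures likewise require the rest of the group to have been numbered already.

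Finally, undosed subjects contribute no post-dose data, no hypothesis is tested (section 16.1.2), and a separate SAP is still to be written (section 16.1.1).

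All of this stands as a limit on the consequences. None of it makes the randomised row correct when a numbered subject is not dosed. Small counts elsewhere hint at a truncated group but do not say how many were randomised or why they were not dosed.

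**Conclusion.** The point holds as a defect in subject accounting. Sections 16.1.5.1 and 16.1.3 together force the randomised row to equal the number dosed, and no other population supplies the true count. That part follows from the text and needs no assumption.

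The size depends on two conditions: numbers are assigned before the Day 1 check or the sentinel decision, and someone is then stopped. Under those conditions a Part A group halted after its sentinels loses 4 of 6 (67%) or 7 of 9 (78%) from the count. These are conditional worst cases for groups dosed with sentinels; in Part B, where Table 4 lists no sentinels, only the Day 1 route applies. If nobody is stopped between numbering and dosing, the table is correct.

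The safety analyses rightly use dosed subjects and do not change. The correction is worth making because it is simple and because the table would otherwise be wrong when a group is cut short.

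**What to change.** In section 16.1.5.1, and in the SAP due before first database lock, change the disposition set from the safety population to all randomised subjects. Show by group: randomised; randomised but not dosed, with reason; dosed; completed; discontinued. List undosed subjects under their randomised treatment, since they have no treatment received, and say whether undosed members of a halted group count as withdrawn. State in section 10.5 when a subject counts as randomised, so that the first row has a definite meaning. Keep the safety population, by treatment received, for all safety analyses.

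The cost is a change of phrase, an extra table row and two clarifying sentences. No new data are needed.
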